This is a multicenter, randomized, clinical trial that will involve a minimum of 480 opiate abusers seeking opiate maintenance treatment. The study will be conducted at 10-12 sites with a maximum of 60 patients enrolled per site. Patients will be recruited at a rate of about 2 per week at each study site. Patient recruitment will last 30 weeks. Patients will remain on study medication for 16 weeks. After eligibility screening and signing a written informed consent, patients will be randomly assigned to one of four treatment groups: buprenorphine 1, 4, 8, or 16 mg/day. About 120 patients will be assigned to each group. Each site will enroll 15 patients into each group.

Patients will be administered their buprenorphine dose daily. No takeout dosages of medication will be allowed. Study sites will dispense buprenorphine 7 days per week.

After patients complete the 16-week protocol, they may be continued on the study drug under a new protocol or offered other treatment available at clinic. Patients who wish to be tapered from buprenorphine will be administered the induction schedule in reverse. If resources are available at the site, eligible patients can be switched to methadone or other treatments available after they are tapered from the buprenorphine. Otherwise, they will be tapered off the drug.

Inclusion Criteria

- 1. DSM-III-R diagnosis of current *opiate dependence* with daily use for past month.
- 2. Male and non-pregnant, non-nursing female, ages 18 or older.
- 3. Mentally competent to give informed consent.
- 4. Agreeable to being in protocol (signs informed consent).
- 5. Permanent residence within commuting distance of clinic.
- 6. Urine negative for methadone.

Exclusion Criteria

- 1. Acute hepatitis or any other acute medical condition that would make participation in the study medically hazardous for the patient, e.g., active tuberculosis, unstable cardiovascular or liver disease, unstable diabetes, or AIDS (not HIV-positive alone). Patients with elevated liver enzymes (SGOT or SGPT greater than 5 times the upper limit of normal) require more frequent clinical and laboratory monitoring than those specified in the schedule of data collection. Those with liver enzymes exceeding 8 times the upper limit of normal require at least weekly clinical and laboratory examinations and consultation from a specialist in liver disease before enrollment.
- 2. DSM-III-R diagnosis of current alcohol dependence or sedative-hypnotics dependence.

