- 3. Current daily use of anticonvulsants, Antabuse, or neuroleptics.
- 4. Patient not expected to remain available to attend clinic for duration of study (e.g., those with criminal charges).
- 5. Patient enrolled in a methadone maintenance program within the past 30 days.
- 6. Has been a patient in a prior buprenorphine trial for treatment of drug addiction.
- 7. Currently participating in another research project.
- 8. Female patient of childbearing potential who refuses birth control.

Patient Screening, Recruitment, and Informed Consent

Patients will be recruited from among opiate dependent patients who apply for treatment at the participating clinics. Figure 2 shows the number of patients that would be active at each site if the patients are recruited at a rate of 2 per week. The top curve shows the number of patients who would be active if all patients remained in the study for the full 16 weeks. The bottom curve is a computer simulation that assumes an overall dropout rate of 30 percent. It will be important for each partici-pating facility to enter a substantial number of female patients. NIDA strives to have at least a third of the patients in their studies be female and requires that at least 25% of study patients are females. Each facility must develop a plan to ensure that sufficient females are entered at their site. This plan might include providing contra-ceptive information and supplies to those women who lack the resources to purchase these supplies themselves.

Screening information needed to ascertain inclusion/exclusion criteria will be collected and recorded on the Study Admission Record (Form 11).

A physician investigator will review the case report forms (Forms 01 to 10) and meet with the potential patient. If the physician determines that the patient satisfies inclusion/exclusion criteria, the physician will discuss the study consent form with the patient. Eligible patients who sign the consent form will become patients in the study when they receive their first dose of buprenorphine.

Randomization

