Principal investigators at each site must agree to data audits by NIDA's Medications Development Division's quality control staff and comply with directions from the Clinical Coordinating Center with regard to protocol compliance and data quality control.

STATISTICAL CONSIDERATIONS

The objective of the proposed study is solely to compare the efficacy of the 8 mg dose of buprenorphine with the 1 mg dose of buprenorphine. The purpose of including the 4 and 16 mg doses of buprenorphine in the trial is to provide additional information about the adequacy of the 8 mg dose and not to prove the efficacy of the 4 mg and 16 mg doses. It is believed that in order to have a successful NDA, information concerning doses other than 8 mg will be required by FDA. Therefore, data on these two additional doses, such as estimates of efficacy parameters and side effects, will be collected to complement the 8 mg versus 1 mg dose comparison.

However, since doses other than 8 mg may be more appropriate for certain subgroup of patients, exploratory analyses as described later will be conducted to identify these subgroups.

Efficacy Variables

Four major efficacy variables will be analyzed. No adjustment in á levels will be made for multiple efficacy variables. These variables will be:

- 1. Incidence of opiate abuse: Since, the incidence of opiate abuse is not directly measurable, a urine sample testing positive for the presence of opiates will be indicative of an episode of opiate abuse. The urine samples will be collected three times a week on Mondays, Wednesdays and Fridays.
- 2. Retention rates: The time from entry in the study to the last dose of buprenorphine administered will be the second major efficacy variable. The reason for termination will be recorded as accurately as possible.
- 3. Opiate craving scores will be measured with a visual analogue scale. The patients will be instructed to record the peak craving that has occurred during the past 7 days. Patients will record their estimate on a 100 mm line designated "no craving" on one end to "most intensive craving I ever had" on the other.

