Percent positive urines will also be calculated for each urine testing opportunity and displayed.

- 2. The total number of positive urines for each patient will be rank ordered according to an algorithm specified by [name] and four preplanned a priori comparisons will be made between the number of positive urines for 1 mg vs. 4, 8 and 16 mg treatments respectively and for 1 mg vs. 4+8+16 mg comparison. Each of these a priori comparisons will be considered to be statistically significant at p value of .05 or below. No adjustment will be made for multiple comparisons.
- 3. ROC curves will be drawn for percent positive urines for each study week for each of the four pairs of treatment groups viz., 1 mg vs. 4, 8 and 16 mg and for 1 mg vs. 4+8+16 mg. No statistical analysis will be performed.

Exploratory Analyses to Identify Subgroups

Subgroups classified by body size/weight, sex and any other quantifiable factor as agreed to by FDA and the sponsor that may affect the suitability of one dose over another will be identified. Percent positive urines for each of these subgroups will be determined to identify which dose may be best for them. Urine sample profiles for all patients will also be displayed to determine which subgroup does better on what dose.

Analysis of Dropout Rates

Cox's single failure proportional hazards model will be used to analyze these data. Treatment assignment, age, sex and study center will be covariates used in the model.

The estimate of \hat{a} (hazard ratio) for treatment assignment adjusted for all other covariates, if found to be statistically significantly different from zero (one) for buprenorphine 8 mg versus buprenorphine 1 mg analysis only at \acute{a} =.05, will be indicative of the superiority of one drug over the other for FDA approval purposes.

Regression coefficients â and hazard ratios for 4 mg vs. 1 mg, 16 mg vs. 1 mg and 1 mg vs. 4+8+16 mg will also be estimated and plotted and displayed for comparison purposes only.

Analysis of Opiate Craving Scores and Global Rating Scores

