This protocol will be reviewed by the IRB of the Grantee Organization, Friends Medical Science Research Center, Inc., and the IRB of the VA Cooperative Studies Program. The principal investigators at each performance site will secure approval of the protocol and consent form from their local IRB. Before patients are entered into the protocol, they must sign the informed consent. A sample informed consent can be found in Appendix A.

PARTICIPATION

The study is to be performed at 12 facilities. Each facility will be expected to enter two patients per week for 30 weeks for a total of 60 patients. If each facility recruits its required number of patients, then there would be 720 patients entered into the trial. This is above the 480 patients required for the study as given in the sample size section. These additional projected patients will give some protection against one or two facilities not producing or a larger than expected loss rate. They would also provide increased power for the study results if all facilities do produce and the loss rate is not excessive.

In addition to providing sufficient patients, each facility must also get IRB or R&D Committee (in the case of VA facilities) approval, be able to administer treatment seven days a week and guarantee to follow all aspects of the study protocol. Facilities not functioning properly may be removed from the study.

The following facilities have agreed to participate in this study:

VAMC, Hines, Chicago, IL Milwaukee Co. Mental Health Complex VAMC, West Haven, CT New York ARTC Philadelphia, PA Pizarro Treatment Center, L.A. San Francisco General Hospital VAMC, San Francisco

VAMC, San Juan, PR West L.A. Treatment Program [name].
[name], M.D., Ph.D.
[name]., Ph.D.
[name], M.D., M.P.H.
[name]., Ph.D.
[name].
[name].
[name].

[name]. [name].

VAOPC, Boston VAMC, New York [name]. [name].

REFERENCES AND BIBLIOGRAPHY

Banks CD: Overdose of buprenorphine: Case report. NZ Med J 1979;89:255-256.

Cohen J: Statistical Power Analysis for the Behavioral Sciences (Second Edition). Lawrence Erlbaum Associates, Publishers, Hillsdale, New Jersey, 1988.

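### The exploratory subgroup step looks for a best dose per subgroup from observed percent positive urines, with no interval and no dose-by-subgroup test, so it cannot separate a real difference from chance

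*Combined protocol and SAP*

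**What the plan says.** Statistical Considerations explains that doses other than 8 mg may suit some patients better and that "exploratory analyses as described later will be conducted to identify these subgroups". The later section, Exploratory Analyses to Identify Subgroups, defines the factors as "Subgroups classified by body size/weight, sex and any other quantifiable factor as agreed to by FDA and the sponsor" where they may bear on the suitability of a dose. It then gives two bases for a conclusion:

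- The first is a set of observed percentages: "Percent positive urines for each of these subgroups will be determined to identify which dose may be best for them"
- The second is a visual display: "Urine sample profiles for all patients will also be displayed to determine which subgroup does better on what dose"

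That is the whole method. There is no interval, interaction test, threshold or limit on the number of factors, and no explicit rule for choosing a dose.

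Other parts of the plan do attach an inferential statement to what they conclude. The pooled urine comparisons under Analysis Primarily for FDA Medical Review have a .05 criterion. The centre subanalysis of the main model is meant to examine treatment-by-centre interaction. The craving and global rating comparisons proceed only if an interaction is absent. The ROC curves are expressly descriptive, and no dose conclusion is drawn from them. Separate male and female subanalyses of the main hazard model are planned, but no dose-by-sex test is stated for them.

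**The concern.** The step compares four doses inside each subgroup and looks for the one that may be best. Observed percentages will almost never tie, so some dose will look best in every subgroup whether or not dose response varies with sex or weight. Two subgroups with the same true dose response can easily have their lowest observed percentages at different doses, most of all when one subgroup is small. At the 25% minimum, women number about 30 per dose.

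At stake is how the output is read. The stated aim is to find patients for whom a dose other than 8 mg may be more appropriate, and the data are to support an NDA. A table of percentages by subgroup and dose, without intervals or an interaction estimate, gives the reader no means of telling a dose-by-sex difference from sampling variation. Each further factor adds another opportunity for an accidental pattern.

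**Working it through.** **Inputs from the documents**

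- Doses: "one of four treatment groups: buprenorphine 1, 4, 8, or 16 mg/day" (Method).
- Arm size: "About 120 patients will be assigned to each group" (Method). If every facility recruits fully, "then there would be 720 patients entered into the trial" (Participation), which is 720/4 = 180 per arm.
- Women: NIDA "requires that at least 25% of study patients are females" and hopes for a third (Patient Screening, Recruitment, and Informed Consent). At 120 per arm this is 30-40 women and 80-90 men per dose.
- Planned effect, 8 mg versus 1 mg (Sample Size Consideration): r = .14 (stated power 60%) and r = .18 (stated power 80%), N = 240. The earlier ARC 090 comparison had p = .015 with 53 and 55 patients.

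**The plan's own figures first.** Noncentral F with 1 and 238 degrees of freedom and λ = f² × 240, at .05:

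- f² = .02: λ = 4.8, power 58.8% (stated 60%).
- f² = .033: λ = 7.92, power 80.0% (stated 80%).
- f² = .15 and .35: above 99.9% (stated 99%).

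These reproduce to within 2 points. The plan gives no figure for the subgroup step.

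**Effect sizes in SD units.** With d = 2r/√(1 − r²):

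- r = .14: 0.28/√0.9804 = 0.28.
- r = .18: 0.36/√0.9676 = 0.37.
- ARC 090: d ≈ 2.43 × √(1/53 + 1/55) = 2.43 × 0.192 = 0.47. This conversion from a p-value is approximate.

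**Probability of different doses.** Assume the dose with the lowest observed percentage is taken in each subgroup, and that the true dose response is identical in men and women. Then

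P(different) = 1 − Σ p_men(j) × p_women(j), summed over the four doses j,

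where p(j) is the chance that dose j has the lowest observed percentage.

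*All four doses equal:* each p(j) = 1/4, so P = 1 − 4 × (1/4)² = 75%.

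*Planned effects:* simulation with normal arm means and equal variance, 120 per arm, 25% women:

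| Assumed common dose response | d = 0.28 | d = 0.37 | d = 0.47 |
|---|---|---|---|
| 4 = 8 = 16 mg, all better than 1 mg | 68% | 67% | 67% |
| Plateau from 8 mg, 4 mg at half effect | 61% | 58% | 55% |
| Linear in log dose to 16 mg | 54% | 47% | 39% |
| 8 mg best, 4 and 16 mg at half effect | 56% | 47% | 35% |

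One cell in full (last row, d = 0.37). The chances of having the lowest percentage at 1, 4, 8 and 16 mg are .033, .176, .616, .175 in women and .003, .091, .815, .091 in men. The products sum to .0001 + .0160 + .5020 + .0159 = .534, so P = 1 − .534 = 47%.

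**Sensitivity**

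- With a third women, or 180 per arm, the same shapes give mostly lower values, down to about 22%.
- Doubling the log-linear effect gives 5-32% across these sizes.
- On an assumed percentage scale (patient SD 25-40 points, 120-180 per dose, 25-33% women), true rates of 75/65/60/55% give 19-46%, and 75/65/60/50% give 2-24%.

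**Comparison.** In the standardised-effect simulations, a 3-degree-of-freedom dose-by-sex interaction test at .05 gave a false signal in about 5% of runs in every scenario.

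**The case against.** The strongest reply is that the section claims little. It is labelled exploratory twice and says only that a dose may be best. The approval claim is confined to 8 mg versus 1 mg, and the 4 and 16 mg arms are expressly not there to prove efficacy. Extra factors need FDA agreement. Nothing sends a subgroup dose to labelling: the directions-for-use language belongs to the extension protocol's changes of method. Separate male and female analyses of the main model are also planned. All of this stands, and it limits how serious the point is. It does not fill the gap, because separate analyses by sex do not test whether dose response differs by sex. Exploratory status can excuse the absence of multiplicity control, but not the absence of any measure of uncertainty beside a suggested dose.

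The second reply is that no lowest-percentage rule is written. That is correct: the probabilities describe one natural reading, and the plan does not oblige anyone to name a dose for every subgroup.

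Third, where two doses are truly equal, disagreement between the sexes is often only a swap between those two, and neither choice is wrong. That also stands for the plateau shapes. It does not apply to the log-linear and 8-mg-best shapes, where one dose is truly best and disagreement is still 35-56%.

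A reader might infer that different doses appear 75% of the time whenever there is no real subgroup difference, or that the plan will nearly always produce subgroup-specific dose statements. The documents support neither. The 75% needs all four doses to be equally effective in everyone, while the plan treats 1 mg as a placebo and is sized on 8 mg beating it.

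**Conclusion.** The point holds as a gap in an exploratory analysis. As written, the step draws suggestions about dose from point percentages and displays over an open list of factors, and provides nothing to tell a dose-by-subgroup difference from chance.

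Under the lowest-percentage reading, men and women with the same true dose response would be given different doses about 35-68% of the time, at 120 per arm, 25% women and effects of the planned size. The limiting value is 75% if the doses do not differ at all. With larger numbers or clear separation between doses the figure can fall to a few percent.

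The range rests on assumed dose-response shapes for 4 and 16 mg, equal variances, approximately normal means and no ties. The documents give no between-patient SD for percent positive urines and no definition of the weight groups, so the figures for sex should not be carried over to weight. The primary comparison is unaffected. This is a cheap improvement.

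**What to change.** For each factor, fit one patient-level model of percent positive with dose, subgroup and dose-by-subgroup terms. Report:

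1. each dose's estimate within each subgroup, with a 95% confidence interval;
2. the interaction p-value;
3. the number of factors examined.

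Show these beside the overall dose response, and describe any subgroup dose difference that the interaction does not support as hypothesis-generating. A strict p < .05 gate on any subgroup remark is not needed: with so few women it would suppress the hypotheses the section exists to raise. The intervals and the interaction estimate are the essential part.

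The cost is a few extra model fits on data already collected and a few sentences in the statistical section. The drawback is low power: with about 30 women per dose the interaction test will miss moderate differences, so fewer firm subgroup statements will be possible.

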- 1. *Urine samples for drugs of abuse* will be collected under observation on Monday, Wednesday, and Friday for each patient. If patient fails to give a sample on the day it is due, it will be recorded as missing. Urine samples will be sent to a central laboratory (University of Utah) to be analyzed for morphine and cocaine or metabolites. An opiate positive will be morphine greater than 300 ng/ml; a cocaine positive will be a cocaine or metabolite greater than 300 ng/ml. All Monday samples (or the first sample collected in a week) will be analyzed additionally for amphetamine, methadone, and benzodiazepines. Study sites will not receive urine results from the University of Utah and study sites are prohibited from locally analyzing urines for drugs of abuse. About half of each urine sample will be frozen at the facilities until the results have been obtained and recorded at the central laboratory.
- 2. Days of retention in treatment is an important measure of treatment effectiveness. If a patient is terminated for any reason, the date of the last buprenorphine dose will be considered the termination date. The reason for protocol termination will be determined as precisely as possible (e.g., medication side effects, arrested, moved from area) and recorded on the study Termination Form (Form 18).
- 3. *Opiate and cocaine craving scores* (Form 13) will be measured with a visual analogue scale. The patient will be instructed to record the peak craving that has occurred during the past 7 days. Patients will record their estimate on a 100 mm line designated no craving on one end and maximum craving ever experienced on the other.
- 4. Global Rating Scores (Forms 04 and 05) are an overall rating of the patient's status at the time of the rating and in comparison to both his/her status at the previous rating and upon entering the study. These scores will be completed by both the patients and the staff. The current status portions of the rating are based on a scale of 0 to 100 with 0 representing an absence of drug problems and 100 representing the worst ever case. The ratings comparing status from the previous rating period are based on a five-point scale where 5 is "much better" and 1 is "much worse."

Other Measures

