- 4. Global Rating Scores are overall ratings of the patients' status at the time of rating (on a scale of 0 meaning no drug problem to 100 meaning worst case ever). These ratings are completed at screening and every four weeks thereafter. The patients are also rated on a scale from 1 (much worse) to 5 (much better) as compared to the previous rating. Both types of ratings are completed separately by the staff as well as the patients. The staff will also be asked to rate the patient at termination in comparison to how the patient was at the time of entry into the study using the five-point scale.

Statistical Methods

Analysis of the Incidence of Opiate Abuse

As mentioned earlier, the incidence of opiate abuse will be estimated by the urine samples obtained and analyzed three times a week, i.e., on Mondays, Wednesdays and Fridays. Thus, in this 16-week maintenance study, up to 48 urine samples will be collected for each patient in the study. However, given the experience with the ARC 090 Study which had as high as 80% dropout rate in the low dose methadone group, the dropout rates are likely to be high and even those who stay in the study are likely to miss a substantial number of clinic visits and, thus, there are likely to be a lot of missing urine samples. In the ARC 090 study, on the average, 20% of the urine samples were missing. Consequently, in order to handle missing values and to simplify statistical analysis, a weekly index of urine positivity for opiates has been developed, or in other words, 48 data points will be reduced to 16 weekly data points. For a given patient, his first study week will be days 1-7 in the study, second study week will be days 8-14 in the study, etc.

The following **data reduction** algorithm will be used:

- 1. If there is at least one positive urine during a given study week, that week will be considered positive for opiates (a *positive week*).
- 2. If all three samples during a week are found to be missing, that week will be considered a *positive week*.
- 3. If conditions 1 and 2 above are not met, the week will be considered to be a *negative week*.

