In a 25-week (17 weeks of maintenance and 8 weeks of detoxification treatment), three-arm study conducted by Addiction Research Center (ARC 090 study), the efficacy of 8 mg buprenorphine was compared with a 20 mg dose of methadone which was considered as a placebo treatment and with 60 mg dose of methadone which was considered as an active control group. It was seen that percents of positive urines observed for buprenorphine were consistently (i.e., over each time point) lower for the maintenance phase of the study than for either the 20 mg or 60 mg methadone groups. The order in which percents positive urines were observed was: (buprenorphine 8 mg) < (methadone 60 mg) < (methadone 20 mg). Even though analysis of variance does not permit analysis of censored observations (as is the case for both ARC 090 and the proposed study), the data for each patient was pooled over time and three treatment groups were compared for percent positive urines. Statistically significant differences were observed for the buprenorphine and methadone 20 mg comparison (p<.001) in favor of buprenorphine. However, no statistically significant differences were observed (p=.78) for the comparison between methadone 60 mg and buprenorphine treatments. This is contrary to what would be expected since buprenorphine treatment resulted in consistently lower percent of positive urines when compared to 60 mg methadone treatment. Obviously, analysis of variance did not result in a test powerful enough to capture the differences between buprenorphine and 60 mg methadone treatment groups. In addition, as mentioned earlier, analysis of variance does not permit the analysis of censored observations. Consequently, analysis of variance will be used to analyze data from the proposed study for medical review only.

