These data will be analyzed by two factor analysis of variance of difference scores \ddot{A}_1 , \ddot{A}_2 , \ddot{A}_3 , etc., where \ddot{A}_1 is the difference in e.g., opiate craving scores at time t_1 and baseline, etc. If no treatment-score interaction is found, four preplanned *a priori* pairwise comparisons will be made between 1 mg and 4 mg, 8 mg, 16 mg and 4+8+16 mg treatments. Separate analyses will be performed for patient and staff ratings.

Secondary Variables

The secondary variables will analyzed using the appropriate statistical methodology. Included in these secondary analyses will be analyses of the number of medical events occurring between the treatment groups. The number of patients reporting any medical events and the number reporting

various specific types of events in each treatment group will be compared using chi-square techniques. Background characteristics of the patients in the treatment groups will be compared using analyses of variance techniques for continuous variables (e.g., age) and chi-square techniques for discrete variables (e.g., gender).

Sample Size Consideration

In the study conducted by the Addiction Research Center (ARC 090 study), the safety and efficacy of buprenorphine 8 mg dose was compared with 20 mg and 60 mg doses of methadone. The 20 mg dose of methadone was assumed to act as a placebo. In the proposed multicenter buprenorphine study, 1 mg dose of buprenorphine will be *assumed* to act as a placebo for statistical purposes. Hence, all sample size calculations will be based on the results obtained from ARC 090 study from buprenorphine 8 mg comparison with 20 mg methadone treatment. Further, since the proposed study intends to compare the safety and efficacy of 1 and 8 mg doses of buprenorphine only, the sample size calculations will be restricted to estimating the group sizes for these two groups only. The purpose of including 4 and 16 mg buprenorphine treatments in the proposed study is to provide additional information regarding the adequacy of 8 mg buprenorphine treatment.

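### Dose comparisons for craving and global ratings depend on an interaction test with no fallback, and the ANOVA behind them is under-specified

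*Combined protocol and SAP*

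**What the plan says.** Under Statistical Methods, Analysis of Opiate Craving Scores and Global Rating Scores, the plan states: "These data will be analyzed by two factor analysis of variance of difference scores". The first such score "is the difference in e.g., opiate craving scores at time t_1 and baseline, etc". The section continues: "If no treatment-score interaction is found, four preplanned" comparisons follow, setting 1 mg against 4 mg, 8 mg, 16 mg and the three combined. Patient and staff ratings are analysed separately.

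The section does not name the two factors, the error term, the level of the interaction test, what happens if an interaction is found, or how missing scores are treated.

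Under Efficacy Variables, both measures are listed among four major variables: "No adjustment in á levels will be made for multiple efficacy variables". On global ratings, item 4 says: "These ratings are completed at screening and every four weeks thereafter". It also describes a second scale: "The patients are also rated on a scale from 1 (much worse) to 5 (much better) as compared to the previous rating". For craving: "The patient will be instructed to record the peak craving that has occurred during the past 7 days". The Schedule of Data Collection shows a screening craving scale (Form 07) and a weekly one in each of weeks 1 to 16 (Form 13).

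**The concern.** A conditional comparison needs a rule for both outcomes of the condition. Here only one is written. If the treatment-score interaction is significant, no test of 8 mg against 1 mg is specified for either variable, and the analyst must choose one after seeing the data. An effect that develops during treatment is one way for that interaction to arise.

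Three further gaps concern the same section:

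- Baseline is used only as a subtraction, which is usually less precise than using it as a covariate.
- The 1-5 ratings have no baseline value to subtract.
- Up to sixteen craving scores come from each patient, and the plan does not say how their correlation enters the error term. Two analysts could follow the text and obtain very different p-values.

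**Working it through.** **Inputs from the documents.** About 120 patients per arm in four arms (Method). Global ratings at screening and weeks 4, 8, 12 and 16, so m = 4 differences per patient. Craving weekly, so up to m = 16.

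**Assumed, because the documents give no figures.** Two-sided 5% tests; complete data; effects in SDs of the change score; equal correlation ρ between a patient's change scores (0.5 in step 1, 0.3 to 0.7 in step 4); baseline-to-visit correlation r from 0.2 to 0.7. The plan states no power or effect size for these variables, so it has no figure to reproduce here; its power table concerns the urine model.

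**1. The interaction condition.** Simulated treatment-by-time ANOVA with the correct split-plot error term, ρ = 0.5. The interaction F has 3(m − 1) and 4 × 119 × (m − 1) degrees of freedom: 9 and 1428 for m = 4, 45 and 7140 for m = 16. The 8 mg effect reaches 0.3 or 0.5 SD, with 4 mg assumed at 0.7 times and 16 mg at 1.2 times that. Chance of a significant interaction, with simulation error of up to about 3 points:

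| Shape of effect over weeks | 4 ratings, 0.3 SD | 4 ratings, 0.5 SD | 16 craving scores, 0.3 SD | 16 craving scores, 0.5 SD |
|---|---|---|---|---|
| Constant | 5% | 5% | 5% | 5% |
| Early onset, 1 − exp(−week) | about 5% | about 5% | 8% | 19% |
| Slower onset, 1 − exp(−week/2) | 5-6% | 5-6% | 20% | 62% |
| Linear growth to week 16 | 29% | 78% | 67% | over 99% |

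In each of those trials a real effect exists and the plan specifies no dose comparison.

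**2. Baseline by subtraction or as covariate.** With equal variance σ² at baseline and visit, the raw change has variance 2σ²(1 − r), and the baseline-adjusted score σ²(1 − r²). The ratio is (1 − r²) / [2(1 − r)] = (1 + r)/2.

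- r = 0.2: 0.96/1.60 = 0.60
- r = 0.3: 0.91/1.40 = 0.65
- r = 0.5: 0.75/1.00 = 0.75
- r = 0.7: 0.51/0.60 = 0.85

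The covariate therefore removes 15% to 40% of the variance of the contrast at a visit.

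**3. The 1-5 ratings.** Efficacy Variables, item 4 defines these against the previous rating, with a staff rating at termination against entry. Each is already a statement of change and has no counterpart at baseline. The analysis section refers to global ratings as a whole and does not separate this scale from the 0-100 scale.

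**4. The unstated error term.** If all scores were treated as independent, the variance of the treatment contrast would be understated by 1 + (m − 1)ρ, and the true level of a nominal 5% test would be 2[1 − Φ(1.96/√(1 + (m − 1)ρ))].

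| ρ | m = 4: factor, level | m = 16: factor, level |
|---|---|---|
| 0.3 | 1.9, 16% | 5.5, 40% |
| 0.5 | 2.5, 22% | 8.5, 50% |
| 0.7 | 3.1, 27% | 11.5, 56% |

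The value ρ = 0.5 is what a shared baseline produces if raw scores are equally correlated at all visits including baseline: covariance σ²(1 − r) over variance 2σ²(1 − r). Simulation gave 38%, 47% and 54% for m = 16. With a patient-level error term it gave 4% to 5% throughout.

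**The case against.** Four stronger readings are tempting, and the documents do not support them.

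- **The ANOVA ignores within-patient correlation.** The text neither states nor excludes a patient-level error term. A treatment-by-time repeated-measures ANOVA fits its wording and holds its level. The inflated levels in step 4 apply only if the scores were treated as independent.
- **The analysis does not adjust for baseline.** Subtraction is an adjustment, and under randomisation the contrast is unbiased. Only precision is lost.
- **There is no test in the expected case.** Baseline is already subtracted and is not a level of the time factor, so arms starting equal does not by itself create an interaction. Under Buprenorphine Induction and Maintenance Procedures every arm is at its assigned dose by day five, and the first global rating after screening is at week 4. An early, stable effect would leave that test near 5%. Nothing in the documents shows growth through week 16.
- **The plan contradicts itself by using ANOVA here after limiting it for urines.** The remark that "analysis of variance does not permit the analysis of censored observations" concerns urine data and stands beside a complaint about power. Craving and rating scores are not censored event times. What remains is that no rule for missing scores is given.

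It is also fair to say that the wording on FDA approval is attached to the urine and dropout models and not to this section. That lowers the severity. It does not supply the missing rule.

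**Conclusion.** The point holds as under-specification with one structural gap. The comparison of 8 mg with 1 mg on two major efficacy variables is conditional, with no alternative stated. How often that matters depends on the shape of the effect over time, which is assumed here: about 5% of trials for a constant effect; still about 5% for global ratings but 8% to 62% for craving with early onset; and 29% to over 99% under linear growth. These figures also rest on ρ = 0.5, complete data and the assumed dose pattern.

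Using baseline only by subtraction forgoes 15% to 40% of the variance at a visit over the assumed r. The difference from baseline is undefined for the 1-5 ratings; that follows from the definitions alone. The unstated error term needs to be named, but no inflation of the type I error has been shown. The change should be made; it is not a condition for the plan's stated approval tests.

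**What to change.** Replace the section's first two sentences with the following.

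- Analyse all observed craving scores and 0-100 global ratings in a mixed model for repeated measures, with patient-level covariance and terms for treatment, week, treatment-by-week, baseline score and centre.
- Test 8 mg against 1 mg, averaged over weeks, whatever the interaction result. Report the interaction descriptively.
- Analyse the 1-5 ratings as observed ordinal scores, without differencing.
- Keep patient and staff ratings separate, as now.

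The cost is SAP wording; all the data are already scheduled for collection. If effects differ by week, the average alone could mislead, so week-specific estimates should be shown with it. Using all observed scores does not remove the need to state the assumption made about patients who drop out.
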